6.2.1.1 Degree of contrast enhancement

A total of up to the 5 largest lesions will be selected and scored by the BRs. The following 4-point scale will be used for lesion enhancement:

- 1 = No lesion is not enhanced
- 2 = Moderate lesion is weakly enhanced
- 3 = Good lesion is clearly enhanced
- 4 = Excellent lesion is clearly and brightly enhanced

The score will be evaluated according to Table 6–1.

6.2.1.2 Border delineation

Up to 5 of the largest lesions will be selected and scored by the BRs.

The following 4-point scale will be used for lesion delineation:

- 1 = None no or unclear delineation of the lesion boundaries
- 2 = Moderate some aspects of border delineation covered
- 3 = Good almost clear, but not complete delineation
- 4 = Excellent clear and complete delineation

The score will be evaluated according to Table 6–1.

6.2.1.3 Internal morphology

Up to 5 of the largest lesions will be selected and scored by the BRs.

The following 3-point scale will be used for lesions:

- 1 = Poor the structure and internal morphology of the lesion is poorly visible
- 2 = Moderate the structure and internal morphology of the lesion is partially visible
- 3 = Good the structure and internal morphology of the lesion is sufficiently visible

The score will be evaluated according to Table 6–1.

6.2.2 Analysis of primary efficacy variables

Analyses of efficacy data will be performed in Full analysis analysis set and Per Protocol analysis set.

The 3 primary analysis variables are derived from the 3 primary visualization parameters below using the following methodology:

- 1. The contrast enhancement (measured on an ordinal 4-point scale)
- 2. The border delineation (measured on an ordinal 4-point scale)

3. The internal morphology (measured on an ordinal 3-point scale)

For the 3 variables, the arithmetic mean lesion score will be calculated for each subject and each BR based on the scores for each individual lesion in a given subject. This average will be the "overall average" for each subject and each BR, and this value will be used for the primary analysis.

For example, BR 1 scores two lesions for subject X. Using border delineation as the example, he scores one lesion as a 3 and the other lesion as a 4. This reader's average lesion border delineation score for subject X will be 3.5 ((3+4)/2). This process is repeated for all 3 BRs. The average of the 3 BR overall averages for subject X is then used for the primary analysis.

The primary efficacy analysis is based on the data from the BRs' evaluation of 3 visualization parameters, which are evaluated in unenhanced and combined unenhanced and enhanced MR image sets.

A successful primary analysis is a demonstration of noninferiority for the difference between the improvement of combined unenhanced/gadobutrol in contrast to the unenhanced vs the improvement of combined unenhanced/gadoterate in contrast to the unenhanced, compared to a reasonable proportion (c = 0.2) of unenhanced vs combined gadoterate for the first 3 primary visualization parameters.

- 1. The contrast enhancement (measured on an ordinal 4-point scale)
- 2. The border delineation (measured on an ordinal 4-point scale)
- 3. The internal morphology (measured on an ordinal 3-point scale)

The analysis for the 3 parameters (1, 2, and 3) will be performed on the mean of the values for the 3 BRs (BR average). This analysis will be performed on the dataset including the subject average ratings for lesions.

For each parameter, a noninferiority hypothesis will be considered, where the comparison will relate to a reasonable portion (c = 0.2) of the difference between combined unenhanced/gadoterate mean and the unenhanced. The goal is to show that the loss in the visualization parameter (gadoterate minus unenhanced) – (gadobutrol minus unenhanced) is lower than 0.2 times the difference between combined unenhanced/gadoterate and the unenhanced mean. "Mean" is the mean of the BR averages.

The null and alternative hypotheses for noninferiority are:

- H_0 : (gadobutrol unenhanced gadobutrol) (gadoterate unenhanced gadoterate) $\leq -0.2*$ (gadoterate – unenhanced gadoterate) vs
- H₁: (gadobutrol unenhanced gadobutrol) (gadoterate– unenhanced gadoterate) > 0.2*(gadoterate unenhanced gadoterate).

The expression "(gadoterate – unenhanced gadoterate)" indicates the difference between combined unenhanced and gadoterate-enhanced mean vs the unenhanced mean.

The study is considered successful if all 3 hypotheses related to these co-primary target variables can be rejected each at a one-sided alpha of 0.025 or equivalently at a two-sided alpha of 0.05. Appropriate paired t-tests will be used as follows

Page: 20 of 29:

The comparisons require calculations of zero-filled averages for each co-primary target variable and each subject for

- (gadobutrol minus unenhanced gadobutrol)
- (gadoterate minus unenhanced gadoterate)

Then, for each subject and each co-primary target variable, a score is derived representing

(gadobutrol minus unenhanced gadobutrol) - 0.8*(gadoterate minus unenhanced gadoterate)

For these scores, means and standard deviations will be calculated. Appropriate t-tests will be applied. For demonstration of noninferiority, p-values will be calculated for the t-test of the working hypotheses

- H₀: (gadobutrol –unenhanced gadobutrol) $0.8*(gadoterate unenhanced gadoterate) <math>\leq 0$
- H_1 : (gadobutrol-unenhanced gadobutrol) 0.8*(gadoterate- unenhanced gadoterate) > 0

One-sided p-values will be calculated and compared to a one-sided alpha of 0.025.

No type I error adjustment for multiple comparisons is needed because tests on all 3 variables must be significant to demonstrate primary efficacy.

In addition, 95% two-sided CIs for the mean difference of the gadobutrol minus unenhanced score and the gadoterate minus unenhanced score will be calculated.

The other set of analysis will compare the combined enhanced and unenhanced image set to corresponding unenhanced image for both gadoterate and gadobutrol to demonstrate the superiority of the combined assessment in these 3 variables. One-sided p-values will be calculated and compared to a one-sided alpha of 0.025. This will be considered as a secondary analysis. Boxplots will be created for visualization.

Subgroup analysis will also be performed to descriptively summarize the improvement of combined unenhanced and enhanced MR image set in contrast to the unenhanced in each of the 3 primary variables (contrast enhancement, border delineation and internal morphology) by the field strength of the MRI device (1.5 or 3.0 Tesla) for gadoterate and gadobutrol groups.

6.2.3 Secondary efficacy variables

The secondary efficacy variables will be the number of lesions identified, the evaluation of the detection of malignant disease and the confidence in diagnosis. The evaluation of quantitative parameters will be performed by General Clinical Imaging Service and image quality will be evaluated by the BR(s).

The secondary efficacy variables are the:

- Comparison of contrast enhancement utilizing an Overall Contrast Enhancement Estimation Algorithm;
- Number of lesions identified (up to 10);

- Identification of benign or malignant disease;
- Confidence in diagnosis;
- Image quality.

6.2.3.1 Overall Contrast Enhancement Estimation Algorithm

Quantitative contrast enhancement estimation will be performed using an exploratory Overall Contrast Enhancement Estimation Algorithm (Relative Contrast Enhancement Score, Full Image Contrast Enhancement Score and Dice Score). The Dice Coefficient is 2 * the Area of Overlap divided by the total number of pixels in both images. The pre-contrast and post-contrast center of mass values will be calculated by the algorithm only for T1w images. The contrast enhancement will be quantified in terms of the relative difference of the centers of masses of ordinary histograms of the unenhanced and enhanced image sets. These results of the algorithm will be summarized by MRI modality using descriptive statistics and 95% CIs.

Subgroup analysis will also be performed to descriptively summarize the estimation scores by the field strength of the MRI device (1.5 or 3.0 Tesla) for gadoterate and gadobutrol groups.

Negative values of Relative and Full Image scores will be set to zero for analyses purposes.

6.2.3.2 Number of lesions able to be identified

For each image set, the BR is to record the total number of lesions, up to 10.

The number of lesions will be set to 11 for analysis purposes if > 10 lesions are reported.

For the number of lesions detected the noninferiority of gadobutrol vs gadoterate will be evaluated using tests or CIs based on the t-distribution. A noninferiority margin of 0.35 will be used in each case. This means that a 95% 2-sided CI for the mean difference gadobutrol score – gadoterate score must exceed the value -0.35 for noninferiority to be achieved.

The null and alternative hypothesis for noninferiority are:

 $H_0:$ combined unenhanced and gadobutrol MRI mean - combined unenhanced and gadoterate MRI mean \leq -0.35, vs

 H_1 : combined unenhanced and gadobutrol MRI mean - combined unenhanced and gadoterate MRI mean > -0.35,

where "mean" is the mean of the BR averages.

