7.2 Dosage and administration

Patients will receive a single dose of gadoterate at the approved dose, 0.1 mmol/kg BW (± 10 percent), via IV bolus administration using a power injector via a peripheral vein (the antecubital vein is preferred). Gadoterate will be injected at a rate of 2 mL/second followed by a 20-mL 0.9% saline flush at the same rate. If the patient is eligible for inclusion in the study, the patient will undergo a second contrast-enhanced MRI using a single dose of gadobutrol 0.075 mmol/kg BW via IV bolus administration using a power injector via a peripheral vein (the antecubital vein is preferred). Gadobutrol will be injected at a rate of 2 mL/second followed by a 20-mL 0.9% saline flush at the same rate.

The administration of gadoterate and gadobutrol is not randomized. During the 24-hour follow-up period after the gadoterate injection and during the 24-hour follow-up period after the gadobutrol injection, no other contrast agent should be given.

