11.4.2.2 Number of lesions able to be identified

A confidence interval for the difference in the number of lesions detected by the 2 contrast agents will be constructed. Noninferiority of number of lesions detected will be demonstrated using confidence intervals based on the t-distribution with a noninferiority margin of 0.35.

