Safety variables will be summarized using descriptive statistics and frequency tables.

All confidence intervals (CIs) will be 2-sided, 95% intervals.

Any statistical tests used for noninferiority will be one-sided tests using the 0.025 level of significance.

The statistical evaluation will be performed by using the software package SAS release 9.2 or higher (SAS Institute Inc., Cary, NC, USA). All variables will be analyzed by descriptive statistical methods. The number of data available and mean, standard deviation, minimum, median, and maximum will be calculated for continuous data. Frequency tables will be generated for categorical data.

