6.2 Efficacy

An overview of the imaging efficacy variables is provided in Table 6–1.

	Unenhanced MRI 1	Combined unenhanced and gadoterate- enhanced MR	Unenhanced MRI 2	Combined unenhanced and gadobutrol- enhanced MRI	Paired gadobutrol- enhanced T1w and gadoterate- enhanced T1w MRI
Variables	BR	BR	BR	BR	BR
Degree of contrast enhancement (lesions)	~	\checkmark	\checkmark	\checkmark	
Assessment of border delineation (lesions)	\checkmark	\checkmark	\checkmark	\checkmark	
Internal morphology (lesions)	\checkmark	\checkmark	\checkmark	\checkmark	
Overall contrast enhancement (Core Lab)	~	~	~	~	
Total number of lesions detected	~	~	~	~	
Malignant Disease		\checkmark		\checkmark	
Confidence in diagnosis		\checkmark		\checkmark	
Image quality					\checkmark

Table 6–1: Overview of the imaging efficacy variables

Abbreviations: BR = blinded reader, MRI = magnetic resonance imaging.

6.2.1 **Primary efficacy variables**

The following 3 lesion visualization parameters scored by three independent BRs constitute the primary efficacy variables:

- Degree of lesion contrast enhancement
- Lesion Border delineation
- Lesion Internal morphology.

As shown in Table 6–1, the independent BRs will evaluate the 3 primary variables (visualization parameters) for up to the 5 largest lesions in each of the following images/image sets separately:

- Unenhanced and combined unenhanced (T1w, T2w, FLAIR) and gadoterate-enhanced (T1w) MR image sets.
- Unenhanced and combined unenhanced (T1w, T2w, FLAIR) and gadobutrol-enhanced (T1w) MR image sets.

The 2 image sets will be evaluated separately in 2 blinded read sessions, with 2 weeks apart between the 2 sessions to prevent reader recall.

For the evaluation of the degree of contrast enhancement, border delineation, and internal morphology, the BRs will score the lesion using the image sequence which best depicts each variable. The scores for multiple lesions of a subject will be handled by zero-filled average method as specified in Section 4.1.

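### The lesion-count noninferiority test cannot separate agent from visit, and the unenhanced counts that could reveal visible change between scans are recorded but never compared.

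*SAP*

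**What the plan says.** Demonstrating noninferiority for number of lesions is a secondary objective (Protocol 4.2, SAP 2.2). SAP 6.2.3.2 sets the alternative hypothesis as "combined unenhanced and gadobutrol MRI mean - combined unenhanced and gadoterate MRI mean > -0.35" and adds: "A noninferiority margin of 0.35 will be used in each case". Protocol 11.4.2.2 describes the same comparison: "A confidence interval for the difference in the number of lesions detected by the 2 contrast agents will be constructed". Neither text contains an unenhanced term. SAP 4.1 sets the error rate: "Any statistical tests used for noninferiority will be one-sided tests using the 0.025 level of significance".

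The unenhanced counts exist. SAP 6.2.3.2 says: "For each image set, the BR is to record the total number of lesions, up to 10". In SAP Table 6-1 the row "Total number of lesions detected" is ticked for Unenhanced MRI 1, Unenhanced MRI 2 and both combined sets. Protocol Table 10-3 shows the same.

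On order, Protocol 7.2 states: "The administration of gadoterate and gadobutrol is not randomized". Protocol 9.2.2 makes gadoterate period 1 and gadobutrol period 2. Protocol 5.1 allows 24 hours to 15 days between injections.

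**The concern.** With a fixed order, the tested difference is the agent effect plus whatever changed between visits. The referral list (Protocol Table 10-1) includes metastases, multiple sclerosis and infectious disease such as brain abscess, so lesions may appear or resolve within 15 days. A net gain could hide a real loss of detection at the reduced dose. A net loss could make an adequate dose look inferior. In either case the result could not be credited to the agent alone.

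The plan holds data that bear on this. A lesion that is new at visit 2 and visible before injection raises the Unenhanced MRI 2 count as well. The SAP supplement compares the two unenhanced sets between visits for the three visualization scores (Tables 16.4/8 to 16.4/10), but not for lesion count, the variable that a new lesion changes most directly.

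**Working it through.** **Plan's own figure.** There is none to reproduce. The documents give no SD, expected difference or power for lesion count. The sample-size text supplies only n: 180 enrolled with about 25% non-evaluable gives 180 × 0.75 = 135.

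**Effect of drift on the planned test.** Let m be the net change in lesions per patient between visits, as counted on the combined sets. The tested mean is the true agent difference plus m. Put the true agent difference at the margin, -0.35, so that every pass is an error. The pass probability is P(T > 1.978), where T is noncentral t with 134 degrees of freedom and noncentrality m × √135 / SD. Here √135 = 11.62. Both m and SD are assumptions.

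| Paired SD | Noncentrality at m = +0.10 | Pass, m = +0.10 | Pass, m = +0.05 | Pass, m = 0 | Pass, m = -0.10 |
|---|---|---|---|---|---|
| 0.75 | 1.549 | 33.7% | 11.7% | 2.5% | 0.02% |
| 1.0 | 1.162 | 21.0% | 8.3% | 2.5% | 0.1% |
| 1.5 | 0.775 | 11.7% | 5.8% | 2.5% | 0.3% |
| 2.0 | 0.581 | 8.3% | 4.7% | 2.5% | 0.6% |

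A gain of 0.10, one extra lesion per ten patients, uses 0.10 / 0.35 = 29% of the margin.

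**What subtraction recovers.** Let v be the share of new lesions visible without contrast. The difference in gains, (combined gadobutrol - Unenhanced MRI 2) - (combined gadoterate - Unenhanced MRI 1), leaves a residual shift of m × (1 - v). A simulation used 135 patients, a mean of 3 lesions, 60% unenhanced detection, 90% gadoterate detection, a gadobutrol deficit of 0.35 and m = 0.10. The planned contrast passed falsely in about 28-30% of trials. The difference in gains passed in about 3% at v = 1 (the no-drift level in that simulation), 10% at v = 0.5 and 30% at v = 0. This setup gave old lesions the same unenhanced detection at both visits, which favours the subtraction.

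**What subtraction costs.** Now suppose that unenhanced detection is independent between visits, with a mean of 3 lesions, 95% combined detection, equal agents and one reader.
- Planned contrast: SD = √(2 × 3 × 0.95 × 0.05) = 0.53.
- Difference in gains: SD = √(2 × 3 × g × (1 - g)), where g = 0.95 - unenhanced detection. For 50%, 70% and 85% unenhanced detection, g = 0.45, 0.25 and 0.10, so SD = 1.22, 1.06 and 0.73.
- For a true deficit of only 0.10, the distance to the margin is 0.25, and power is roughly Φ(0.25 × 11.62 / SD - 1.96). The planned contrast has above 99%. The difference in gains has about 66%, 78% and 98%.

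**Does own-visit subtraction protect the co-primary scores?** The score in SAP 6.2.2 is "gadobutrol minus unenhanced gadobutrol) - 0.8*(gadoterate minus unenhanced gadoterate" (outer brackets dropped). SAP 4.1 zero-fills across agents. Suppose one lesion scores 1 unenhanced and 3 combined at both visits. The score is 2 - 0.8 × 2 = 0.4. Add a lesion present only at visit 2, scoring 1 then 3. The gadobutrol gain is (6 - 2) / 2 = 2. In the gadoterate sets the new lesion is filled with zeros, so that gain is (3 - 1) / 2 = 1. The score becomes 2 - 0.8 × 1 = 1.2. The new lesion does not cancel.

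**The case against.** - **The planned contrast is a legitimate question.** The number of lesions seen on each agent's complete study is what the protocol asks about, and the SAP supplement defends direct comparison of combined sets as consistent with clinical practice. This stands, and it is why the planned test should stay. The difference in gains asks about lesions seen only because of contrast, and nothing in the documents justifies 0.35 as a margin for it.
- **Change between visits is limited.** The 15-day cap and exclusion criteria 7, 9 and 10 (Protocol 6.3) restrict instability, treatment changes and procedures. They reduce change, but they neither exclude natural progression nor measure it.
- **The unenhanced counts are not wholly ignored.** SAP 4.1 promises descriptive statistics for all variables, which would cover each unenhanced count separately. The paired difference, and any use in comparing agents, is still absent.
- **The direction is open.** A reader might infer that the design favours gadobutrol. The documents do not support that: resolving lesions count against it, and so may entry only after an enhancing lesion is seen on the gadoterate scan.
- **The co-primary scores.** A reader might also infer that they are safe because each subtracts its own unenhanced set, leaving lesion count as the sole exposed endpoint. Zero-filling across agents defeats that, as the example shows.

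**Conclusion.** The concern holds as an attribution problem in a secondary endpoint. The planned test credits or charges gadobutrol with any net change in lesions between visits, and the recorded data that could show the visible part of that change go unused. The 8-34% false-pass range is conditional on 135 evaluable patients, a true deficit exactly at the margin, a net gain of 0.10 lesion and a paired SD between 2.0 and 0.75. None of the drift or SD values comes from the documents, so these figures show sensitivity and do not estimate the bias. The study's success criterion, which rests on the three visualization scores, does not depend on this test.

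One might go on to require both intervals to exclude -0.35. The evidence does not support that: the second interval would borrow an unjustified margin, could lose a good deal of power, and gives no protection against new lesions seen only after contrast.

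**What to change.** Keep the planned contrast and the 0.35 margin as the test. Add to SAP 6.2.3.2, for each reader and for the reader average:

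1. The paired difference, Unenhanced MRI 2 count minus Unenhanced MRI 1 count, with a 95% CI, as a check for drift.
2. A supportive sensitivity analysis of (combined gadobutrol - Unenhanced MRI 2) - (combined gadoterate - Unenhanced MRI 1), with a t-based 95% CI.

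State in advance that if item 1 shows drift, or item 2 disagrees with the planned result, the lesion-number conclusion will be qualified as possibly reflecting change between visits. Do not make item 2 a second mandatory criterion. If these are added after the results are known, as the SAP supplements were, label them post hoc.

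The cost is SAP wording and one or two table rows, with no new patients, scans or reads. Item 2 may have a wider interval, and it removes only change visible without contrast.

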6.2.3.3 Identification of benign or malignant disease

Up to 30 days post first MRI the site investigator will record in the eCRF his final clinical diagnosis, see Table 6–2 and if it confirms that the subject has malignant disease. This will serve as SOT for malignancy. A summary of final clinical diagnosis will be presented for total subjects in FAS and PPS.

The BRs will evaluate the presence of malignant lesions for each subject for the combined unenhanced and gadobutrol-enhanced MR image sets, and the combined unenhanced and gadoterate-enhanced MR image sets separately.

Page: 22 of 29:

The SOT will be compared to the blinded read evaluations individually and per majority of BRs (at least 2 out of 3 readers).

Table 6–2: Final clinical diagnosis of CNS lesions

Meningioma Chordomas • Anaplastic/malignant meningioma Primary lymphoma Glial tumor, low grade (I/II) Dermoid/Epidermoid tumors . Glial tumor, high grade (III/IV) Infectious disease (e.g., brain abscess, . cisticercosis, etc.) Glial tumor, tumor grade cannot be Venous angiomas • determined Metastases Meningeal spread of meningiomas (dural • involvement) Multiple sclerosis (acute and chronic) Cerebellopontine angle tumors . **Optic neuritis** Von Hippel Lindau syndrome Meningeal disease (focal enhancement) Hypertensive leukoencephalopathy Pituitary adenomas (macro and micro) Subacute/chronic ischemia • • Craniopharyngiomas Encephalitis • • Tumors of the choroid plexus Others, specify Tumors of the pineal gland Not assessable . Meningeal carcinomatosis Oligodendrogliomas grade II Oligodendrogliomas grade III (anaplastic/malignant)

Abbreviations: CNS = central nervous system

Diagnoses of the presence or absence of malignant tumors in each subject will be evaluated for consistency with the final diagnosis. Proportions of diagnoses consistent with the final diagnosis regarding malignancy will be calculated for gadobutrol and gadoterate, and a CI based on McNemar's test for the difference of these proportions will be given. The noninferiority of gadoterate to gadobutrol will be claimed using a noninferiority margin of 10%. These analyses will be performed for sensitivity, specificity, and overall accuracy.

Table 6–3 displays the components of the definitions for sensitivity, specificity, and accuracy.

Reader Response for MRI	Final clinical diagnosis (Standard of truth)			
	Malignant	Not Malignant		
Malignant	True positive (TP)	False positive (FP)		
Not Assessable	Not assessed positive (NAP)	Not assessed negative (NAN)		
Not Malignant	False negative (FN)	True negative (TN)		

Table 6–3: Components of the definitions for sensitivity, specificity, and accuracy

Sensitivity will be calculated as the number of subjects identified by MRI to have malignant lesions divided by the total number of subjects with malignant lesions according to the truth standard. Specificity will be calculated as the number of subjects identified by MRI to have no malignant lesion divided by the total number of subjects with no malignant lesion according to the truth standard. Accuracy will be calculated as the number of subjects correctly identified by MRI as having or not having malignant lesions, divided by the total number of subjects. For this analysis, a response of Benign will be considered as Not Malignant. When a response is neither benign nor malignant, then this will be considered as Not Assessable.

Using the notation of the above table,

Sensitivity = TP/(TP + NAP + FN);

Specificity = TN/(TN + NAN + FP);

Accuracy = (TP + TN)/(TP + TN + NAP + NAN + FP + FN).

Note that these calculations consider nonassessable segments as incorrect.

For the computation of the asymptotic CIs, McNemar's test-based CIs for the difference of rates between both MRI sets, the definitions in Table 6–4 are needed. With this, the standard

error of the difference between p₂ and p₁ is defined as $SE_{p_2-p_1} = \sqrt{(p_1 + p_2 - (p_1 - p_2)^2)^2 \frac{1}{n}}$

Then, the 95% asymptotic CI of the difference between p_2 and p_1 can be computed as $[(p_2 - p_1) - z_{0.975} \cdot SE_{(p_2 - p_1)}] + z_{0.975} \cdot SE_{(p_2 - p_1)}]$, with $z_{0.975} = 1.96$ as the corresponding quantile of the standard normal distribution.

Table 6–4: Components of confidence interval

Combined unenhanced/gad	Combined unenhanced diagnoses agree w		
oterate- enhanced diagnoses agree with final diagnoses	Yes	Νο	
Yes	Number of subjects with matches to final diagnosis for both MRI sets: a	Number of subjects with a match for gadoterate MRI set but not for gadobutrol MRI set: b	Proportion of subjects with a match in gadoterate MRI set: p ₁ = (a+b)/n
No	Number of subjects with a match for gadobutrol MRI set but not for gadoterate MRI set: c	The number of subjects without a match for either MRI set: d	
	Proportion of subjects with a match in gadobutrol MRI set: p ₂ = (a+c)/n		n = a+b+c+d

Abbreviations: MRI = magnetic resonance imaging.

The match to final diagnosis will be always considered regarding presence or absence of malignancy.

For comparing sensitivity between modalities, the match to final clinical diagnosis refers to malignancy = yes, so n in Table 6–4 will be the total number of subjects with malignant final clinical diagnosis by the investigator (SOT).

For comparing specificity between modalities, the match to final clinical diagnosis refers to malignancy = no, so n in Table 6–4 will be the total number of subjects with benign final clinical diagnosis by the investigator (SOT).

For accuracy, the match to final clinical diagnosis refers to true positive (TP) and true negative (TN) regarding malignancy, so n will be the total number of subjects with any final clinical diagnosis by the investigator (SOT); this will be sum of the entries for each field of the tables above for sensitivity and specificity.

These tables will be produced for each reader and for the majority reader. Majority reader is defined as the value of at least two out of three readers.

Note that truth panel diagnoses of other and not assessable will be excluded from McNemar's test or calculation of McNemar's test-based CIs.

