11.4.2.3 Identification of benign or malignant disease

The investigator determines if the patient has benign or malignant disease.

The presence or absence of malignant disease in each patient for both contrast agents will be determined by the blinded readers, as well as the majority blinded reader (at least 2 of 3 readers), and compared to the investigators' assessment to calculate sensitivity and specificity for each drug.

Sensitivity, specificity, and accuracy for each drug will be compared using a McNemar's test with a noninferiority margin of 10 percent.

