Below is a list of documents this statistical analysis plan (SAP) is based on:

- Protocol Amendment 1.0, dated on 26 MAR 2018
- eCRF Final 2.0, dated on 06 Mar 2018.

2. Study Objectives

2.1 **Primary Objectives**

The primary objective of this study is to demonstrate noninferiority of gadobutrol-enhanced CNS imaging (at a dose of 0.075 mmol/kg BW) compared to gadoterate (0.1 mmol/kg BW) -enhanced CNS imaging (at a dose of 0.1 mmol/kg BW) for 3 lesion visualization parameters (degree of contrast enhancement, assessment of border delineation, and internal morphology of lesions) based on a blinded read.

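### The noninferiority claim for sensitivity, specificity and accuracy is written backwards (gadoterate noninferior to gadobutrol), so it is easiest to meet when the reduced dose performs worst

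*SAP*

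**What the plan says.** SAP 6.2.3.3 compares each agent's diagnoses with the investigator's final diagnosis and gives the claim as: "The noninferiority of gadoterate to gadobutrol will be claimed using a noninferiority margin of 10" percent. It then sets the scope: "These analyses will be performed for sensitivity, specificity, and overall accuracy".

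The same section defines p1 in Table 6–4 as the gadoterate match rate and p2 as the "Proportion of subjects with a match in gadobutrol MRI set". The confidence interval is for p2 − p1, gadobutrol minus gadoterate. The section gives no null or alternative hypothesis and does not say which limit is compared with which bound.

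Protocol 11.4.2.3 gives the margin without a direction: "Sensitivity, specificity, and accuracy for each drug will be compared using a McNemar's test with a noninferiority margin of 10 percent".

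Elsewhere gadobutrol is the agent under test. SAP 2.1 reads "The primary objective of this study is to demonstrate noninferiority of gadobutrol-enhanced CNS imaging", with gadoterate as comparator. For lesion counts, SAP 6.2.3.2 reads "For the number of lesions detected the noninferiority of gadobutrol vs gadoterate will be evaluated", with both hypotheses written out and a bound of −0.35.

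**The concern.** Noninferiority is not symmetric. The agent named first has to be shown not to lose more than the margin against the agent named second. Here that is the standard-dose comparator, so the claim would show that gadoterate is not much worse than reduced-dose gadobutrol. That says nothing about whether the lower dose costs diagnostic performance.

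Three secondary claims rest on this sentence, each made per reader and for the majority reader. Taken literally, each becomes easier as gadobutrol loses accuracy and harder as it gains. A programmer who follows the text tests the wrong limit. One who silently reverses it departs from the prespecified rule.

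**Working it through.** **Passages side by side**

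| Place | Agent to be shown noninferior | Bound stated |
|---|---|---|
| SAP 2.1, primary objective | gadobutrol | – |
| SAP 6.2.2, primary hypotheses | gadobutrol | −0.2 × gadoterate gain |
| SAP 6.2.3.2, number of lesions | gadobutrol | −0.35 |
| Protocol 11.4.2.3, diagnostic measures | not stated | 10 percent, no sign |
| SAP 6.2.3.3, diagnostic measures | **gadoterate** | 10%, no sign |

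The SAP supplement returns to this analysis to correct the standard error but leaves the sentence alone. The change history in SAP section 7 does not mention it.

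**Translating the two claims.** Put D = p2 − p1.

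- As written: gadoterate is noninferior if the lower limit of p1 − p2 exceeds −0.10, which is the same as the **upper limit of D below +0.10**.
- As the trial needs: gadobutrol is noninferior if the **lower limit of D is above −0.10**.

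**Inputs.** The interval is D ± 1.96 × SE, with the supplement's SE = √{[(b + c)/n − D²]/n}. Here b is the number correct on gadoterate only and c the number correct on gadobutrol only. A two-sided 95% limit matches the one-sided 0.025 level in SAP 4.1. The documents give no expected rates, discordance or malignant/benign split for these measures, so there is no planned figure to reproduce and the tables below are assumed.

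**A case to check by hand.** a = 60, b = 25, c = 5, d = 10, n = 100:

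- p1 = 85/100 = 0.85; p2 = 65/100 = 0.65; D = −0.20
- SE = √[(0.30 − 0.04)/100] = √0.0026 = 0.0510
- 95% CI = −0.20 ± 0.100 = −0.300 to −0.100
- As written: −0.100 < +0.10, so the claim is **met**
- Trial's direction: −0.300 is below −0.10, so the claim is **not met**

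Two contrasting tables with n = 100:

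| a, b, c, d | D | 95% CI | As written | Trial's direction |
|---|---|---|---|---|
| 65, 5, 25, 5 (gadobutrol better) | +0.20 | 0.100 to 0.300 | not met | met |
| 80, 5, 5, 10 (equal) | 0 | −0.062 to 0.062 | met | met |

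**Probability of each claim.** Simulation of 200,000 paired tables per setting, at n = 40, 60, 80 and 135. The largest n is the whole evaluable sample, 180 × 0.75 = 135.

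| True D | Assumed discordance | As written | Trial's direction |
|---|---|---|---|
| −0.20 | 25% | 99–100% | 0.1% or less |
| −0.10 (on the intended margin) | 15% | 95–100% | 4–6% |
| 0 | 10% | 57–95% | 57–95% |
| +0.10 | 15% | 4–6% | 95–100% |

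**Second set of assumptions.** Gadoterate sensitivity 80%, within-pair correlation about 0.4, n = 50 to 135:

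| Gadobutrol sensitivity | As written | Trial's direction |
|---|---|---|
| 60% | 99–100% | under 0.1% |
| 70% | 87–99.9% | 3–4% |
| 85% | 18–29% | 76–99% |

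**The case against.** The strongest reply is that two drug names were transposed and the plan as a whole shows what was meant. The secondary objective for sensitivity and specificity (Protocol 4.2, SAP 2.2) sets reduced-dose gadobutrol against standard gadoterate. Protocol 10.6 describes testing gadobutrol against an approved comparator. The interval is oriented as gadobutrol minus gadoterate. The upper-limit rule is printed nowhere; it is inferred from the literal wording. Trial success depends only on the three primary hypotheses, which run the right way. Both proportions and the interval would be reported, so a 20-point loss would be visible. The percentages also depend on assumptions: at n = 50, with pairing correlation from 0 to 0.6, a true gadobutrol rate of 70% meets the written claim 64–97% of the time. And 135 malignant subjects would leave none for specificity.

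Most of this stands. A slip is the likely explanation, the primary result is untouched, and the percentages are illustrative. What does not follow is that the text can stay. The upper-limit rule is the only translation of the words at the 10-point margin, and inferring the intended direction means overriding the one sentence that states it. In every setting examined, the written claim is met more often as gadobutrol gets worse. Only at D = 0 do the two readings pass equally often.

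One qualification concerns the standard error. The formula in SAP v3.0, as it reads in the available text, gives much wider intervals. For a = 45, b = 15, c = 0, d = 15 it gives an upper limit of +0.108, so even the written claim fails. The supplement's formula gives −0.291 to −0.109 for that table. The supplement replaces the earlier formula, so it was used throughout.

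**Conclusion.** The concern holds. The only sentence giving these three endpoints a claim direction reverses the trial's question, and nothing in the protocol, SAP or supplements corrects it. The reversal follows from the text and needs no assumption.

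Its size does need assumptions. With the rates and discordance above, a true 10-point loss, the largest the intended margin contemplates, meets the written claim in 95–100% of trials, against 4–6% in the trial's direction. A true 10-point gain meets it in only 4–6%.

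The effect is confined to secondary noninferiority claims. The estimates, the sample size and the primary conclusion do not change. Until the sentence is corrected, a statement that the diagnostic noninferiority criterion was met cannot be read as support for the reduced dose.

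**What to change.** Replace the sentence in SAP 6.2.3.3, or correct it in a supplement, with: noninferiority of gadobutrol to gadoterate is claimed, separately for sensitivity, specificity and accuracy, if the lower limit of the two-sided 95% CI for p2 − p1 (gadobutrol − gadoterate) is greater than −10 percentage points, using the supplement's corrected standard error. Add the hypotheses in the form used for number of lesions: H0: p2 − p1 ≤ −0.10 against H1: p2 − p1 > −0.10.

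Because the supplements describe their analyses as post hoc, enter this as a dated correction. State that the 10% margin is unchanged from Protocol 11.4.2.3 and which limit the analysis program actually compared. The cost is one sentence, two hypotheses and a program check. No new data are needed.
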